1 **25/10/2022**

2

3 **Retraining the automatic reaction to physical activity and sedentary stimuli in adults 60 years of**  
4 **age or older: A cognitive bias modification protocol**

5

6 **ABSTRACT**

7 **Background:** To counteract the pandemic of physical inactivity, current interventions mainly rely on  
8 reflective processes that focus on increasing the motivation to be physically active. Yet, while these  
9 interventions successfully increase intention, their effect on actual behavior is weak. Recent findings  
10 suggest that this inability to turn the intention into action is explained by negative automatic reactions to  
11 stimuli associated with physical activity. These automatic reactions could be particularly strong in older  
12 adults, who are more likely to associate physical activity with fear, pain, or discomfort. **Objective:** The aim  
13 of this program is to test the effect of an intervention that targets the automatic processes underlying  
14 physical inactivity in older adults. Training older adults to inhibit the automatic attraction toward sedentary  
15 stimuli is hypothesized to increase physical activity, thereby contributing to improving physical functioning  
16 and quality of life. **Methods:** To test these hypotheses, older adults will be enrolled in a controlled double-  
17 blinded study with a 1, 3, 6, and 12-month follow-up. Participants will be randomized (1:1 ratio) to receive  
18 a 12-session cognitive-bias modification training for 3-week based on a go/no-go task in an experimental  
19 or a control condition (placebo). The primary outcome will be the number of steps per week. Secondary  
20 outcomes include automatic approach-avoidance tendencies, explicit affective attitudes toward physical  
21 activity, physical function, and quality of life. **Discussion:** The study is expected to inform public-health  
22 policies and improve interventions aiming to counteract the pandemic of physical inactivity.

23

24 **KEYWORDS:** Attentional Bias, Aging, Exercise, Sedentary Behavior

25 **Background**

26 Over the past two decades, society has encouraged people to be more physically active [1-3]. As a  
27 result, most individuals are now aware of the positive effects of regular physical activity and have the  
28 intention to exercise [4]. Yet, this intention is not sufficient, as exercise plans are often not executed [5].  
29 Despite gradually scaling up actions that promote physical activity over the years, people are becoming less  
30 active. From 2010 to 2016, the number of inactive adults has increased by 5% worldwide, currently  
31 affecting more than 1 in 4 adults (1.4 billion people) [6]. This gap between intention and action is a  
32 challenge that health professionals need to address in order to counteract the pandemic of physical inactivity  
33 [7, 8].

34 Physical activity is one of the top contributors to health, reducing rates of cardiovascular disease  
35 [9], cancer [10], hypertension [11], diabetes [12], obesity [13], and depression [14]. This wide spectrum of  
36 benefits is particularly important for older adults, who often suffer structural and functional deterioration  
37 in several physiological systems. Physical activity can reduce and delay the impact of this age-related  
38 deterioration in health [15] and functional independence. However, in the Americas, more than 60% of  
39 older adults are physically inactive [16]. Current interventions to enhance physical activity in older adults  
40 rely mainly on reflective processes by providing rational information about the health benefits of a  
41 physically active lifestyle [17]. From this perspective, changing conscious goals should lead to substantial  
42 behavioral change [18]. Yet, meta-analyses indicate that these interventions are more effective in changing  
43 intentions than actual behavior [19]. Thus, new interventions targeting alternative processes (e.g., automatic  
44 processes) are needed.

45 The engagement in physical activity is governed not only by reflective processes, but also by  
46 automatic affective reactions acting outside conscious awareness [20]. For example, in active individuals,  
47 stimuli associated with physical activity attract attention [21, 22], trigger positive affective reactions [23,  
48 24], and activate approach tendencies [25]. These automatic reactions are thought to facilitate the translation  
49 of intention into action. From this perspective, physical inactivity is the result of an imbalance between  
50 strong negative automatic reactions to stimuli associated with physical activity and a relatively weaker  
51 intention to be physically active. This imbalance between reflective and automatic processes can be  
52 particularly pronounced in older adults, who are more likely to spontaneously associate physical activity  
53 with fear, pain, or discomfort felt during physical exercise. Therefore, older adults could be particularly  
54 responsive to and benefit the most from an intervention targeting the automatic reactions to physical activity  
55 and sedentary stimuli.

56 Interventions targeting automatic reactions to health-related stimuli have already proven to be  
57 successful in changing behavior [26-32]. For example, interventions have been used to retrain the automatic  
58 reaction to alcohol [27]. Using a joystick, patients were repeatedly asked to avoid pictures on a screen that

59 were related to alcohol and to approach pictures unrelated to alcohol. Results showed that adding to a  
60 regular treatment an intervention targeting cognitive bias reduced the relapse rates one year after treatment  
61 discharge by 9% to 13% [27-29]. These interventions have also proven to be useful in impacting smoking  
62 [30], social anxiety [31], and eating behavior [32]. Based on these encouraging results, the current project  
63 proposes to test the effect of a cognitive-bias intervention on another health behavior: physical activity.

64 **Primary aim**

65 The overall primary objective of this project is to investigate the effectiveness of an intervention  
66 targeting automatic reactions to physical activity and sedentary stimuli in older adults.

67 **Secondary aim**

[figure not shown]
68 The secondary objective is to test the effects of the intervention on reflective and automatic  
69 processes underlying physical activity, physical functioning, and quality of life.

70

71 **Methods**

72 **Study design and settings**

73 Our study follows a placebo (sham-controlled), double-blinded design with a 12-month follow-up  
74 (Figure 1).

75

**Figure 1.** Study design

76

77 ***Participants***

78 Older adults aged 60 years and older will be enrolled in the study.

79 ***Recruitment***

80 Recruitment will occur by placing posters in a: strategic areas, such as public areas where permissible and  
81 b: posting on social media (Facebook, Twitter). Interested seniors will be asked to contact the researcher  
82 directly. Once the interested person initiates the contact leaving a phone message or sending an e-mail, we  
83 will follow up on them and will invite them to attend in an in-person meeting aiming to increase their  
84 intention to be physically active based on the “Ask-Assess-Advise” approach and to inform them about the  
85 study. Participants will receive a copy of the consent form prior to the first meeting so that they know from  
86 the onset what the study entails. Interested participants will be given an opportunity to ask any question  
87 over the phone or in the meeting before written informed consent is obtained. Consent will be only obtained  
88 once the participant has fully understood what the study entails and accept to take part in the study. If they  
89 decide to participate, they can withdraw from the research at any time and/or refuse to answer any questions,  
90 without suffering any negative consequences.

91 ***Eligibility***

92 To participate in this study, volunteers must be 60 or over 60 years old and able to understand  
93 instructions in English. We will not include people who a: present diagnosed psychiatric disorders or  
94 neurological pathologies (cardiovascular accidents, Parkinson’s or Alzheimer’s disease, dementia), b:  
95 unable to carry out the training program, or unable to understand the protocol, c: having motor deficit  
96 preventing physical activity without external help, d: having physical health status preventing physical  
97 activity and, e: alcohol or substance dependence.

98 ***Sample size***

99 Based on a meta-analysis reporting the effect size of interventions using the go/no-go task ( $g = .39$ )  
100 [32, 33], a desired statistical power of .9, and an alpha of .05 [34], a sample size calculation indicated that  
101 a minimum of 108 patients per condition is needed.

102 ***Ethics and dissemination***

103 This research will be performed in accordance with the Declaration of Helsinki. The study was  
104 approved by the University of Ottawa (Canada) Research Ethics Boards (H-09-22-8453). Potential  
105 participants will be informed of study details, including procedures, risks and benefits, confidentiality, and  
106 the voluntary nature of participation, before signing the consent form. Data will be kept on the uOttawa  
107 OneDrive, with access limited to team members. This system is protected by multi-factor authentication,  
108 meets Personal Health Information Protection Act requirements, and is serviced by the uOttawa

109 cybersecurity team. To guarantee that the research output is fully accessible to the public, the manuscripts  
110 will be published as preprints (e.g., SportRxiv) and data, material, and scripts will be made publicly and  
111 freely available on open repositories (e.g., Zenodo). Results will be published in relevant scientific journals  
112 and be disseminated in international conferences.

113 ***Intervention***

114 **Cognitive-bias modification task**

[figure not shown]
115 The intervention of the proposed project is based on a go/no-go task in which older adults need to  
116 quickly decide whether or not they should react to a stimulus [40]. The task has been adapted to train  
117 inhibitory processes counteracting the automatic attraction to sedentary stimuli and to promote the  
118 automatic approach to stimuli related to physical activity. Specifically, a rectangle containing an image, or  
119 a word will be presented on a screen.

120 **Intervention group**

121 In the intervention group, older adults will be instructed to restrain their actions when the rectangle  
122 is tilted to the right and to react by pressing a key on the keyboard when the rectangle is tilted to the left,  
123 irrespective of the content of the rectangle (because the training is meant to be implicit). In order to train  
124 inhibitory processes counteracting the automatic attraction to sedentary behavior, 90% of the rectangles  
125 tilted to the right (counterbalanced across participants) will contain a picture or a word related to sedentary  
126 behavior (Figure 2). To foster the automatic attraction toward physical activity, 90% of the rectangles tilted  
127 to the left will contain a picture or a word related to physical activity.

128 **Control group**

129 In the comparison group, instructions will be identical, but the percentage of physical activity and  
130 sedentary stimuli will be equal in each tilt condition (i.e., 50% sedentary stimuli and 50% physical activity  
131 stimuli in both right- and left-tilted rectangles) (Figure 2).

[figure not shown]

133 **Figure 2.** Go/No-go task based on images (left panel) and words (right panel).

134

135 **Experimental protocol**

136 Participants will be invited to attend a meeting aiming to increase their intention to be physically  
137 active based on the “Ask-Assess-Advise” approach [17] and to inform them about the study. Those who  
138 accept to participate will receive a physical activity tracker (GT9X-BT) [41]. Participants will be trained  
139 for 3 weeks (4 sessions/week) in the go/no-go task (Figure 3). Each training session will consist of 2 blocks  
140 of 400 trials for a total of 30 min. To assess the effect of the intervention, primary and secondary outcomes  
141 will be collected for one week, the week before the first session, the week following the last session of the  
142 intervention, as well as 1, 3, 6, and 12 months post intervention.

143

144 **Figure 3.** Protocol timeline.

145

146 ***Allocation and blinding***

147 Participants and research assistant will be blinded to the groups’ allocation. The participant blinding  
148 success will be appraised by asking them to guess in what group there were at the trial termination. Besides,  
149 the research assistant blinding success will be appraised via detecting the group allocation (Experimental  
150 vs. Control) by research assistant at the end of data collection phase. The randomization will be generated  
151 on a computer and an independent coworker will carry out the randomization. The participant’s  
152 identification number will be used to determine the sequence of randomization. Participants will be  
153 randomized in a 1:1 ratio between the intervention and active control condition.

154

155 ***Outcomes***

156 Participants will first respond to questions related to their age, sex (male, female), weight, and  
157 height.

158 ***Primary outcome***

159 The project focuses on device-based measures of physical activity and sedentary behaviors.  
160 Specifically, the primary outcomes collected using a physical-activity tracker will be the number of steps.  
161 Participants will be given the tracker and will be trained on how to wear the device (ie, over the right hip,  
162 affixed to an elastic belt, preferably worn under their waistbands). Currently, the waist based Actigraph is  
163 the most used device to objectively measure physical activity. Participants will be instructed to used it all

164 day long for 7 days and not to used it during shower or when they sleep at night. If the participant uses the  
165 tracker less than for 4 days in a row for at least 7 hours per day, they will not be included in the study. The  
166 number of steps measured in the week pre- and post-intervention, as well as 1, 3, 6, and 12 months after the  
167 intervention will be used as the primary outcome.

168 ***Secondary Outcomes***

169 The secondary outcomes will allow the examination of indirect health effects related to an increase  
170 in physical activity and a decrease in sedentary behavior.

171 **1. Reflective and automatic processes underlying physical activity**

172 (a) *Explicit Affective Attitude Toward Physical Activity*: Explicit attitudes toward physical activity will  
173 be calculated as the mean of two items (Cronbach's alpha = 0.92) based on two bipolar semantic  
174 differential adjectives on a 7-point scale (unpleasant-pleasant; unenjoyable-enjoyable). The  
175 statement begins with "For me, to participate in regular physical activity is ..." [42].

176 (b) *Approach-avoidance task*: A contextual approach-avoidance task will be used to measure  
177 automatic approach and avoidance tendencies toward physical activity and sedentary behaviors  
178 [36]. Participants will be asked to move a manikin on the screen "toward" (approach condition)  
179 and "away" (avoidance condition) from images depicting physical activity and sedentary behaviors  
180 by pressing keys on a keyboard. Each trial will be started with a black fixation cross presented  
181 randomly for 250–750 ms in the center of the screen with a white background. Then, the manikin  
182 will be appeared in the upper or lower half of the screen. Concurrently, a stimulus depicting  
183 "movement and active lifestyle" (i.e., physical activity) or "rest and sedentary lifestyle" (i.e.,  
184 sedentary behavior) will be presented in the center of the screen. Participants quickly must move  
185 the human figure "toward" a stimulus (approach) depicting physical activity and "away" from a  
186 stimulus (avoidance) depicting sedentary behaviors, or vice versa. After seeing the manikin in its  
187 new position for 500 ms, the screen will be cleared. In case of an incorrect response, error feedback  
188 (i.e., a cross) will be appeared at the center of the screen.

189 **2. Physical Functioning**

190 (a) *Usual Level of Moderate-to-Vigorous Physical Activity*: The usual level of physical activity  
191 will be derived from the short form of the International Physical Activity Questionnaire  
192 (IPAQ-SF). The IPAQ-SF is a self-administered questionnaire that identifies the frequency  
193 and duration of moderate and vigorous physical activity, as well as sedentary time during the  
194 past 7 days to estimate usual practice of physical activity and sedentary behavior [46]. The  
195 usual level of moderate-to-vigorous physical activity (MVPA) in minutes per week will be  
196 used as a control variable in the analyses.

197 (b) *6-Minute Walk Test*: The 6-minute walk test (6MWT) has been adopted as the most widely  
198 used functional test of exercise capacity given its ease of administration and its ability to  
199 reflect function during daily activities. Additionally, the 6-minute walking distance is widely  
200 used for measurement of treatment response in clinical practice and clinical trials. The test is  
201 conducted by having the participant walk as far as possible on a flat indoor course for a period  
202 of 6 minutes. Standardized encouragement will be provided at each minute. Total distance  
203 walked in 6 minutes will be documented. The major outcome is the distance walked during  
204 the 6 minutes. The major advantages of the 6MWT are that the test requires minimal technical  
205 resources and involves a familiar daily activity [44].

206 (c) *Hand grip strength*: Hand grip strength will be assessed with a dynamometer. Participants  
207 will perform the test using their reported dominant hand in a seated position. Two tests would  
208 be performed by each participant and the higher value will be recorded as hand grip strength  
209 [45].

210 **3. Quality of Life**

211 (a) *World Health Organization Quality of Life (BREF)*: The scale assesses quality of life over four  
212 domains: Physical Health (seven items), Psychological Health (six items), Social Relationships  
213 (three items), and Environmental Health (eight items). Scores for each domain can range from  
214 zero to 100, with higher scores indicating better QoL [46].

215 ***Data collection and management***

216 All information will be gathered by research assistant. All identifying information from the study  
217 data will be eliminated by using a code so that the identity will not be directly associated with the data the  
218 participant provided. Each participant will be given a unique confidential identification code upon they  
219 accept to take part in the study. All data including coded information will be kept in OneDrive account of  
220 principal investigator which is protected by a two-factor authentication. The confidentiality of the  
221 information collected will be guaranteed by using this unique confidential code for data storage and  
222 analyses. Storage will be maintained for 10 years after the end of the study.

223 ***Data analyses***

224 ***Primary analysis***

225 Statistical analyses will be performed according to the intention-to-treat principle and abide by the  
226 Consolidated Standards of Reporting Trials (CONSORT) guidelines. A sequential analysis will be  
227 conducted with an interim analysis after 50% of the data is collected and the other analyses after all data is  
228 collected [47]. Based on the Pocock boundary, the threshold for significant p-values will be .0294 [48]. If  
229 the effect is significant at the interim analysis, thereby indicating that the data provide support for the

230 hypothesis, data collection will be terminated. Mean, SD, median and range values will be used to  
231 summarize the continuous data. The primary outcome (number of steps per week) will be analyzed using  
232 multiple linear regressions. Particularly, we will test whether the participants' physical activity level  
233 (number of steps) the week after intervention termination will be higher in the intervention group relative  
234 to the control group, after adjustment for covariates (i.e., age, sex). Furthermore, we will test whether  
235 participants' automatic approach tendencies towards physical activity will be higher and participants'  
236 automatic approach tendencies towards sedentary behaviours will be lower in the intervention group  
237 compared to the control group.

238 *Secondary Analysis*

239 The continuous outcomes will be analyzed using linear mixed-effects models, which account for  
240 the nested structure of the data (i.e., multiple observations within a single participant), thereby providing  
241 accurate parameter estimates with acceptable type-I error rates [49]. To examine the effect of the  
242 intervention on the evolution of physical activity and sedentary behavior, models will include interaction  
243 terms between group (intervention group vs. comparison group) and number of days within or after (follow-  
244 up) the intervention. We will treat the continuous secondary outcomes in the similar way to the primary  
245 outcome. R software will be exploited for all analyses.

246 ***Data Monitoring***

247 The principal investigator will instruct all project team members to ensure that the study will be  
248 carried out according to the protocol. Research assistants will need to understand the protocol before  
249 starting the data collection. The ethics committee may visit the research sites for quality assurance. No  
250 serious adverse event resulting from the intervention is expected; however, all potential adverse events will  
251 be documented.

252

253 **Discussion**

254 Most individuals are aware of the benefits to health of regular physical activity and have good  
255 intentions to exercise. Yet, 1.4 billion people worldwide are inactive, which suggests that turning intention  
256 into action can be challenging. Recent findings show that the intention-action gap could be explained by  
257 negative automatic reactions to stimuli associated with physical activity. This gap is particularly concerning  
258 in older adults, who are more likely to spontaneously associate physical activity with fear, pain, or  
259 discomfort. Current interventions targeting physical activity largely focus on providing rational information  
260 to alter individuals' conscious goals. However, these strategies have been shown to be insufficient to change  
261 a behavior and urge that automatic reactions towards physical activity-related stimuli would be involved in  
262 the physical activity regulation. Therefore, to promote physical activity, the current project proposes to train  
263 older adults to suppress their automatic attraction toward sedentary stimuli and to respond positively to

264 physical-activity stimuli. The intervention is expected to reduce physical inactivity during the intervention  
265 and at follow-up, thereby improving physical functioning. More broadly, the output of this program has the  
266 potential to develop an evidence-based, large-scale, low-cost intervention that would complement current  
267 reflective approaches in older adults to improve their quality of life. Finally, the results will inform public  
268 health policies aiming to counteract a global health problem: The pandemic of physical inactivity.

269

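### The consecutive-days wear rule rejects some fuller weeks of step data while keeping thinner ones, and the plan does not say which weeks it covers

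*Combined protocol and SAP*

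**What the plan says.** All references are to the combined protocol and SAP.

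- **Recording window (Primary outcome).** Participants are told to wear the tracker all "day long for 7 days and not to used it during shower or when they sleep at night".
- **Wear rule (same paragraph).** If the participant uses the "tracker less than for 4 days in a row for at least 7 hours per day, they will not be included in the study".
- **Weeks measured (next sentence).** The outcome is the "number of steps measured in the week pre- and post-intervention, as well as 1, 3, 6, and 12 months after the" intervention, so there are six recording weeks.
- **Analysis (Primary analysis).** "The primary outcome (number of steps per week) will be analyzed using" multiple linear regression. The test is whether steps in "the week after intervention termination will be higher in the intervention group relative" to control, adjusted for age and sex.
- **Principle (Primary analysis).** "Statistical analyses will be performed according to the intention-to-treat principle".

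The plan gives no reason for requiring consecutive days. It does not say which of the six weeks the rule governs, or how a week with fewer than 7 valid days becomes a weekly step count. The Sample size section states 108 per condition as a minimum and mentions no allowance for lost data.

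**The concern.** Thresholds of 4 days and 7 hours are a matter of judgement and are not disputed here. The consecutive-days condition is a separate matter. It can rank weeks against the amount of data they hold: a person who misses only day 4 has six valid days in runs of 3 and 3 and fails, while a person who wears the device on days 1 to 4 and then stops passes. A weekly total or mean makes no use of adjacency.

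What is at stake depends on when the rule is applied:

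- **Pre-randomisation week only.** Suitable volunteers are turned away needlessly.
- **Post-intervention or follow-up weeks.** Randomised participants with usable data are removed because of how they wore the device after allocation. That contradicts the intention-to-treat statement and reduces the analysed number below 108 per arm.

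**Working it through.** **1. The plan's own figure.** The wear rule has no figure attached, so the only one to reproduce is 108 per arm, used below as the base for power. With n = 2(z_alpha + z_beta)² / g², g = .39, power .90 and alpha .05:

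- one-sided: 2(1.645 + 1.282)² / .1521 = 112.6, so 113
- two-sided: 2(1.960 + 1.282)² / .1521 = 138.2, so 139
- one-sided with g rounded to .40: 17.13 / .16 = 107.1, so 108

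The stated 108 is matched only by the last line. That is a separate matter, but it explains why the power figures in step 5 start below 90%.

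**2. Pattern counts.** All 2^7 = 128 valid/invalid patterns were enumerated, a valid day being one with at least 7 hours' wear.

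| Valid days | Patterns | Kept: 4 in a row | Rejected: 4 in a row | Kept: any 4 of 7 |
|---|---|---|---|---|
| 4 | 35 | 4 | 31 | 35 |
| 5 | 21 | 9 | 12 | 21 |
| 6 | 7 | 6 | 1 | 7 |
| 7 | 1 | 1 | 0 | 1 |

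Every week kept by the run rule is also kept by any 4 of 7. The counts need no assumption, but they are counts of patterns, not shares of participants.

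**3. Loss with independent days (daily wear p is assumed).** A first run of 4 starts on day 1, or on day 2, 3 or 4 after an invalid day, so P(run of 4 or more) = p⁴[1 + 3(1 − p)]. P(any 4 of 7) is the upper binomial tail.

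| p | Fail run rule | Fail any 4 of 7 |
|---|---|---|
| .95 | 1 − .8145 × 1.15 = 6.3% | 0.02% |
| .90 | 1 − .6561 × 1.30 = 14.7% | 0.3% |
| .85 | 1 − .5220 × 1.45 = 24.3% | 1.2% |

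Independence scatters the gaps and so favours the concern.

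**4. Loss with clustered wear.**

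- *Some people wear the device reliably, others do not.* Let p vary between persons as Beta(a, b) with intraclass correlation .4, so a = 1.5p and b = 1.5(1 − p) for mean p. A given pattern with k valid days has probability B(a + k, b + 7 − k) / B(a, b). Summing over kept patterns, retention under the run rule against any 4 of 7 is .923 against .966 (p = .95), .847 against .928 (.90) and .772 against .885 (.85). The extra loss is 4.3, 8.1 and 11.3 percentage points.
- *Gaps run together in time.* With a lag-1 correlation of .6 between days, retention is 89.2% against 94.0% at p = .90 (4.8 points) and 77.2% against 85.4% at p = .80 (8.2 points).

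**5. Power, if the rule applies to the post-intervention week.** There are two looks, at 50% and 100% of the data, each at p < .0294 two-sided (critical z = 2.178). The final statistic has mean θ = g√(n/2), the interim statistic has mean θ√.5, and their correlation is √.5.

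- 108 per arm: θ = .39√54 = 2.866, power 77.6%
- 97 per arm (108 × .90 = 97.2): θ = .39√48.5 = 2.716, power 72.9%

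The plan does not state sidedness. With a one-sided .0294 threshold at both looks, the same loss takes power from 85.4% to 81.8%. With a single one-sided .05 test, it goes from 88.9% to 85.8%.

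**The case against.** The strongest reply is that non-inclusion in the study is the language of eligibility, and that the schedule has a tracker week before the first session. Read as a baseline screen, the rule loses no outcome data from randomised participants, does not touch power if 108 per arm are still enrolled, and does not conflict with intention to treat. This stands as a possible reading. It is not the only one: the sentence sits in the outcome section, directly before the list of six recording weeks, with no restriction to the first. Nor do the documents say whether randomisation comes before or after the baseline week. A reader might infer that the plan breaches intention to treat; the text supports that only conditionally.

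Three further objections also stand in part:

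- A reader might infer that everyone with five or six valid days is discarded. That is wrong: 9 of 21 five-day patterns and 6 of 7 six-day patterns pass.
- The losses rest on assumed wear rates, and independence gives the largest ones. The 10% used for power is near the top of the clustered range. Part of the shortfall from 90% power comes from the sample-size calculation, not from wear.
- That consecutiveness brings no measurement gain is an inference. It is a reasonable one, since no analysis uses day order and a four-day run does not even secure a weekend day (Monday to Thursday passes), but the documents do not state it.

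A reader might also infer bias between arms. Both arms face the same rule, and nothing in the documents shows a differential effect.

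**Conclusion.** The point holds in a conditional form. It is certain from the text that the rule can reject a week with five or six valid days and keep one with four, and that the planned analyses make no use of adjacency. The consequence depends on timing that the plan leaves open: avoidable screen-outs if the rule is confined to the week before randomisation, or loss of randomised participants, lower power and a conflict with intention to treat if it reaches later weeks.

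The size is illustrative only. With clustered wear averaging 85% to 95% of days, the extra loss is about 4 to 11 percentage points per recording week. A 10% loss in the primary-analysis week costs 4.7 power points two-sided (77.6 − 72.9), and 3.1 to 3.6 points in the one-sided variants. The documents support no firm estimate of lost data. This is a worthwhile correction, not a threat to the trial's validity.

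The same sentence leaves two related gaps, in the derivation of a weekly count and the handling of randomised participants with too little wear. On the first, an unscaled four-day sum would be 4/7 = 57% of a full week at the same daily activity.

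**What to change.** Four changes to one paragraph, keeping the sponsor's thresholds of 4 days and 7 hours:

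1. Replace the consecutive-days condition with: *fewer than 4 valid days (at least 7 hours) of the 7, not necessarily consecutive*.
2. Define the outcome as mean steps per valid day, multiplied by 7, so that weeks with different numbers of valid days are comparable.
3. State which of the six weeks the rule covers, and whether randomisation comes before or after the baseline week.
4. After randomisation, treat a failing week as missing for that visit and keep the participant in the analysis. The primary regression uses a single week, so the plan should also name how a missing post-intervention value is handled.

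The cost is a few sentences, with no extra visits or equipment. The downside is that slightly more varied sets of days contribute to each weekly mean. If the sponsor has a reason for requiring consecutive days, it should be stated and the expected loss allowed for in the sample size.
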